Study subjects will receive a single treatment dose (at Day 0) in addition to SOC antibiotic treatment, and then enter a safety, efficacy and PK follow-up study period for a total study duration of 28 days. The selection of SOC antibiotics is made in accordance with local best practices at the discretion of the investigator and should not exceed the duration of 14 days.

The clinical course of pneumonia will be assessed daily by the investigator. Once Clinical Cure has been determined, the clinical status of the subject will be monitored to confirm continuation of Clinical Cure, re-infection (pneumonia due to *P. aeruginosa*), or new infection (pneumonia due to an unknown pathogen or a pathogen other than *P. aeruginosa*). "Clinical Cure" will be declared at any time during the study by the PI, provided that the required criteria are met either based on documented improvements in signs and symptoms, +/- changes documented by chest X-ray (if performed as part of SOC), as interpreted by the investigator.

The assessment of Clinical Cure (resolution of pneumonia) by the site investigator will be used for the primary analysis. An adjudication committee will apply newly defined Clinical Cure criteria post hoc in a secondary analysis. “Clinical Cure” will be assessed for analytical purposes on Day 7, 14, 21 (primary efficacy endpoint) and 28.

Clinical safety assessments will be performed on an ongoing basis while predefined laboratory assessments will be performed at baseline, and thereafter at Day 4, 7, 14, 21, and 28. Test results obtained for medical reasons between these mandatory time points will be assessed for adverse events and documented accordingly.

Secondary efficacy endpoints will be assessed in a similar manner during the 28-day period when appropriate, daily when possible, (e.g., Time on mechanical ventilation including if tracheostomy is in place; Time on supplemental oxygenation; measures of respiratory health such as changes in PaO₂/FiO₂ using arterial blood gases and/or pulse oximetry measurements), or upon occurrence (e.g., antibiotic utilization, duration of stay in the ICU, duration of hospitalization, duration of intubation with ventilation, or duration of mechanical ventilation if tracheostomy in place).

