Visit	Screening, Baseline, and Randomization	Treatment	Follow-up (Daily until index pneumonia is considered resolved)	Follow-up Any setting	End of Study ¹⁴ or Early Termination ¹⁷
Day	-1	0	1 to 28 Daily	4, 7, 14, 21	28 or Day of Termination
Informed Consent	X				
Eligibility	X				
Demographics	X				
Type of Pneumonia ¹⁰	X				
Medical history	X				
Surgical History	X				
Case history	X				
Concomitant medications	X	X	X	X	X
Physical exam	X			X	X
Vital signs ¹¹	X	X	X	X	X
12-lead ECG	X				
Safety laboratory tests	X		X ¹	X	X
Sampling: ADA	X ³				X
Sampling: Future Biomarkers (where applicable)				X	X
Sampling: PK	X ⁴	X ^{5,6}	X ^{5,6}	X ^{5,6}	X ^{5,6}
Microbiology: rapid testing	X				
Microbiology: classic	X		X ¹	X ¹	X ¹
Sampling: microbiology	X		X ¹	X ¹	X ¹
Respiratory data	X	X ²	X ¹	X	X
Arterial gases or pulse oximetry ¹⁶	X	X		X	X
PaO ₂ /FiO ₂ ratio	X	X	X	X	X
APACHE II	X				
SOFA	X	X	X ²		
Randomization	X ⁷				
Treatment		X			
Assessment of Clinical Cure			X ⁸	X	X
Adverse events		X	X	X	X
Chest X-Rays	X ¹²				
Pregnancy Test (Urine or Serum)	X ¹³				
Discharge data					X ⁹
Study Follow-Up Phone Call				X ¹⁵	X ¹⁵

Visit	Screening, Baseline, and Randomization	Treatment	Follow-up (Daily until index pneumonia is considered resolved)	Follow-up Any setting	End of Study ¹⁴ or Early Termination ¹⁷
Day	-1	0	1 to 28 Daily	4, 7, 14, 21	28 or Day of Termination

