
 1. To be performed if medically necessary. Follow-up airway specimens to be obtained as medically necessary and prior to extubation and at Day 28 (if not extubated prior to then) for quantitative or semi-quantitative culture. 2. SOFA and respiratory data to be collected on Day 0, 12 hours after treatment initiation and on Day 4, 7, 14, 21, 28 while intubated and mechanically ventilated. Parameters for SOFA score calculation should not be older than 72 hours. 3. ADA only at screening / baseline and Day 28, or at early termination. 4. Pre-dose PK sample to be obtained prior to treatment initiation. 5. PK samples to be obtained for the FULL PK sub-study at the following times after initiation of treatment: 2 hours (end of infusion), 4h, 12h, and 24 hours and 1 sample at each of the following visits: Day 4, 7, 14, 21, and 28. 6. PK samples for the SPARSE PK sub-study at the following times after initiation of treatment: 1 sample at 2 hours (end of infusion), 1 sample at either 4h, 12h, or 24 hours post-treatment initiation (inclusive) and 1 sample at any of the following visits: Day 4, 7, 14, 21, or 28. 7. Eligible subjects are randomized on Day -1, Treatment day is Day 0 for the purpose of monitoring and collecting the required samples over the first 24 hours. 8. Clinical Cure will be assessed at Day 7, 14, 21, 28 for the analytical purposes. 9. Discharge data to be obtained when discharge occurs or Day 28, whichever occurs first. 10. Patients with pneumonia who are intubated are eligible for screening regardless of the type of pneumonia, which will be recorded at the time of screening for all study subjects. 11. Vital signs will be recorded at baseline prior to treatment (time 0) and then at 1, 2, 4, 12, and 24 hours post treatment. Vital signs will also be recorded daily thereafter. 12. In addition to the screening timepoint, chest x-ray(s) are to be taken at any time as medically indicated. 13. Women of child bearing potential must take a urine or serum pregnancy test at the time of Screening. 14. For subjects with early discharge, effort must be made to perform all protocol defined procedures outlined for End of Study/Early Termination. 15. Subjects who decide to discontinue study assessments prior to Day 28 will receive a study exit safety follow-up phone call on key days (Day 4, 7, 14, 21, 28) until Day 28 (+7 days) to assess Clinical Cure, survival and the status of any adverse events. 16. Changes in PaO₂/FiO₂ ratio (e.g. by arterial blood gases), if available and whenever possible OR changes in non-invasive measures of oxygenation (e.g. by pulse oximetry) 17. A few days before or after the specified date is acceptable (± 2 days) 					

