8.3 Adverse Events

An adverse event is defined as any untoward medical occurrence in a clinical investigation subject administered a pharmaceutical product, which does not necessarily have a causal relationship with this treatment. An adverse event can therefore be any unfavorable and/or unintended sign (including an abnormal laboratory finding), symptom, or disease temporally associated with the use of an investigational medicinal product, whether or not related to the investigational medicinal product. All adverse events, including observed or volunteered problems, complaints, or symptoms, are to be recorded on the appropriate electronic case report form (eCRF).

Adverse events, which include clinical laboratory test variables, will be monitored and documented from the time of randomization until 28 days after last dose. Subjects should be instructed to report any adverse event that they experience to the Investigator. Beginning at Day 0, Investigators should make an assessment for adverse events at each visit and record the adverse event on the appropriate eCRF using the EDC system.

Wherever possible, a specific disease or syndrome rather than individual associated signs and symptoms should be identified by the Investigator and recorded on the eCRF using the EDC system. However, if an observed or reported sign or symptom is not considered a component of a specific disease or syndrome by the Investigator, it should be recorded as a separate adverse event. Additionally, the condition that led to a medical or surgical procedure (e.g., surgery, endoscopy, tooth extraction, or transfusion) should be recorded as an adverse event, not the procedure.

Any medical condition already present prior to Day 0 should be recorded as a pre-existing condition in the Medical History, and not be reported as an adverse event. However, should the medical condition or signs or symptoms present at baseline change in severity or seriousness at

any time after randomization or during the study, an adverse event should be reported (worsening of pre-existing condition).

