8.5 Serious Adverse Event Reporting – Procedures for Investigators

Initial Reports

Serious adverse events will be reported in compliance with country-specific regulatory requirements relating to safety reporting to the regulatory authority IRB/EC and investigators.

All SAEs occurring from randomization until 28 days following the last administration of study drug must be reported to the Contact Research Organization (CRO) Clinical Safety within 24 hours of the knowledge of the occurrence (this refers to any adverse event that meets any of the aforementioned serious criteria). All SAEs that the Investigator considers related to study drug occurring after the 28-day follow-up period must be reported to the Aridis Pharmaceuticals Inc.

To report the SAE, complete the SAE form electronically in the EDC system for the study. When the form is completed, CRO Safety personnel will be notified electronically and will retrieve the form. If the event meets serious criteria and it is not possible to access the EDC system, send an email to CRO Safety at [contact] or call the CRO SAE hotline (phone number listed below), and fax/email the completed paper SAE form to CRO (fax number listed below) within 24 hours of awareness. When the EDC system becomes available, the SAE information must be entered within 24 hours of the system becoming available.

Safety Contact Information: Clinical Safety

SAE hotline – USA:

[contact], dial 3 or [contact], dial 3

[contact] or [contact]

Email: [contact]

SAE hotline – Europe:

[contact]

[contact]

Email: [contact]

Follow-Up Reports

The Investigator must continue to follow the subject until the SAE has subsided or until the condition becomes chronic in nature, stabilizes (in the case of persistent impairment), or the subject dies.

Within 24 hours of receipt of follow-up information, the Investigator must update the SAE form electronically in the EDC system for the study and submit any supporting documentation (e.g., subject discharge summary or autopsy reports) to Clinical Safety via fax or e-mail. If it is not possible to access the EDC system, refer to the procedures outlined above for initial reporting of SAEs.

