
 
1. To be performed if medically necessary. Follow-up airway specimens to be obtained as medically necessary and prior to extubation and at Day 28 (if not extubated prior to then) for quantitative or semi-quantitative culture.
 
2. SOFA and respiratory data to be collected on Day 0, 12 hours after treatment initiation and on Day 4, 7, 14, 21, 28 while intubated and mechanically ventilated. Parameters for SOFA score calculation should not be older than 72 hours.
 
3. ADA only at screening / baseline and Day 28, or at early termination.
 
4. Pre-dose PK sample to be obtained prior to treatment initiation.
 
5. PK samples to be obtained for the FULL PK sub-study at the following times after initiation of treatment: 2 hours (end of infusion), 4h, 12h, and 24 hours and 1 sample at each of the following visits: Day 4, 7, 14, 21, and 28.
 
6. PK samples for the SPARSE PK sub-study at the following times after initiation of treatment: 1 sample at 2 hours (end of infusion), 1 sample at either 4h, 12h, or 24 hours post-treatment initiation (inclusive) and 1 sample at any of the following visits: Day 4, 7, 14, 21, or 28.
 
7. Eligible subjects are randomized on Day -1, Treatment day is Day 0 for the purpose of monitoring and collecting the required samples over the first 24 hours.
 
8. Clinical Cure will be assessed at Day 7, 14, 21, 28 for the analytical purposes.
 
9. Discharge data to be obtained when discharge occurs or Day 28, whichever occurs first.
 
10. Patients with pneumonia who are intubated are eligible for screening regardless of the type of pneumonia, which will be recorded at the time of screening for all study subjects.
 
11. Vital signs will be recorded at baseline prior to treatment (time 0) and then at 1, 2, 4, 12, and 24 hours post treatment. Vital signs will also be recorded daily thereafter.
 
12. In addition to the screening timepoint, chest x-ray(s) are to be taken at any time as medically indicated.
 
13. Women of child bearing potential must take a urine or serum pregnancy test at the time of Screening.
 
14. For subjects with early discharge, effort must be made to perform all protocol defined procedures outlined for End of Study/Early Termination.
 
15. Subjects who decide to discontinue study assessments prior to Day 28 will receive a study exit safety follow-up phone call on key days (Day 4, 7, 14, 21, 28) until Day 28 (+7 days) to assess Clinical Cure, survival and the status of any adverse events.
 
16. Changes in PaO2/FiO2 ratio (e.g. by arterial blood gases), if available and whenever possible OR changes in non-invasive measures of oxygenation (e.g. by pulse oximetry)
 
17. A few days before or after the specified date is acceptable (<math>\pm 2</math> days)
 
					

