## 5.2. Secondary Clinical Efficacy Endpoints

The secondary clinical efficacy endpoints are the following:

1. Proportion of patients with Clinical Cure at Day 28
2. Proportion of patients with Clinical Cure at Day 14
3. Proportion of subjects who died (All-cause mortality) at Day 28
4. Proportion of subjects who died due to pneumonia (Pneumonia-related mortality) at Day 28
5. Proportion of patients with Clinical Cure at Day 7
6. Change from baseline in respiratory functional assessment: Time on mechanical ventilation (including if tracheostomy is in place). Time on supplemental oxygenation. Measures of respiratory health such as changes in PaO2/FiO2, using arterial blood gases and/or pulse oximetry measurements.
7. Mean change from baseline in overall clinical status measured by SOFA scores.
8. Health economics: antibiotic utilization, duration of stay in the ICU, duration of hospitalization, duration of intubation with ventilation or duration of mechanical ventilation if tracheostomy is in place.

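### The ± 2-day window on the Day 28 visit lets a subject finish on Day 26 with no required check of vital status or adverse events on or after Day 28

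*Protocol*

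**What the plan says.** **The window.** The last column of Protocol Table 6-1 covers End of Study or Early Termination, with the day given as "28 or Day of Termination". Footnote 17 on that column reads "A few days before or after the specified date is acceptable (± 2 days". SAP Table 1 repeats it.

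**What runs to Day 28.**
- Mortality. SAP 5.2 lists "Proportion of subjects who died (All-cause mortality) at Day 28" and the matching pneumonia-related endpoint. They are third and fourth in the testing order (SAP 6.4.2) and are tested with a stratified CMH test (SAP 6.4.2.2).
- Adverse events. Protocol 8.3 says they "will be monitored and documented from the time of randomization until 28 days after last dose".
- Serious adverse events. Protocol 8.5 says "All SAEs occurring from randomization until 28 days following the last administration of study drug must be reported".

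**What happens at the last visit.** Protocol 6.7 records all-cause mortality there and asks that AE outcomes be final. Table 6-1 schedules nothing later for a subject who attends.

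**Other subjects.** Those who stop assessments early are telephoned "until Day 28 (+7 days) to assess Clinical Cure, survival and the status of any adverse events" (Table 6-1, footnote 15; also Protocol 8.8). Cured and discharged subjects who cannot come to the clinic are telephoned on the key visit days, including Day 28 (Protocol 8.8).

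**The concern.** The same schedule uses two kinds of window for the same time point. The call for early leavers can only fall on or after Day 28, so it secures survival and AE status for the full period. The visit for completers can fall before Day 28, and nothing then requires a second contact. For a subject seen on Day 26, a death or event on Day 27 or 28 reaches the database only if the site learns of it some other way, which is least certain after hospital discharge.

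At stake are the completeness of two tested secondary endpoints and the last two days of the defined safety period. The SAP sets no analysis window for Day 28 and no rule for vital status last known on Day 26 or 27, so how such a subject enters the mortality rate is left open.

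**Working it through.** The plan states no figure on this point, so there is none to reproduce. The check is calendar arithmetic, followed by a scale calculation on stated assumptions.

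**1. Calendar.** The single dose is on Day 0 (Protocol 3.1), and the full PK schedule places the Day 28 visit at 672 hours (Protocol 7.4.1): 672 / 24 = 28 days. So 28 days after the dose means Day 28. The visit window is 28 − 2 = Day 26 to 28 + 2 = Day 30. A close-out on Day 26 covers 26 / 28 = 92.9% of the period, a shortfall of 2 days.

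**2. Who must be contacted on or after Day 28?**

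| Subject | Required contact | Reaches Day 28? |
|---|---|---|
| Pneumonia not resolved | Daily, Days 1 to 28 (6.5) | Yes |
| Stopped assessments early | Call, Day 28 to Day 35 (8.8, footnote 15) | Yes |
| Cured, discharged, cannot attend | Call on key days including Day 28 (8.8) | Yes |
| Cured, attends on Day 26 or 27 | None after the visit | Not required |

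Only the last row is open. It need not be a small group: daily assessment stops once the pneumonia is judged resolved, and the sample size section assumes 65% and 85% cured at Day 21, an average of 75% with equal arms. How many of these would attend early is unknown.

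**3. Scale for mortality.** The assumptions, none from the documents, are Day 28 mortality *m* of 15%, 25% or 35% and a constant hazard. The planned 154 randomized subjects are used for scale.

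λ = −ln(1 − m) / 28

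P(death between Day 26 and Day 28) = exp(−26λ) − exp(−28λ)

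- m = 0.15: λ = 0.00580; 0.8599 − 0.8500 = 0.99%; × 154 = 1.53
- m = 0.25: λ = 0.01027; 0.7656 − 0.7500 = 1.56%; × 154 = 2.40
- m = 0.35: λ = 0.01539; 0.6703 − 0.6500 = 2.03%; × 154 = 3.13

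These are ceilings: every subject closed on Day 26 and no later death learned of. Scaled by the share actually closed on Day 26:

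| Share closed on Day 26 | m = 15% | m = 25% | m = 35% |
|---|---|---|---|
| 100% | 1.53 | 2.40 | 3.13 |
| 50% | 0.76 | 1.20 | 1.56 |
| 25% | 0.38 | 0.60 | 0.78 |
| 10% | 0.15 | 0.24 | 0.31 |

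Widening *m* to 10-50% moves the ceiling to 1.0-3.9 deaths. Relative to all deaths by Day 28, the ceiling is 1.53 / (0.15 × 154) = 6.6% at the low end and 3.13 / (0.35 × 154) = 5.8% at the high end.

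The exposed subjects have been judged cured and are well enough to attend, so their hazard is probably below the average used here. Halving it roughly halves each entry.

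**The case against.** **A visit window does not end the observation period.** This stands. A reader might infer that a subject closed on Day 26 is simply not observed afterwards. The documents do not support that: AE and SAE duties are set by date and footnote 17 does not shorten them, death meets the seriousness criteria in Protocol 8.4, and Protocol 4.3 asks that collection continue through Day 28 after improvement or ICU discharge. The defensible statement is that events on Days 27 and 28 need not be actively ascertained. A duty to report what the site knows is not a required contact that would find it.

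**Such a subject is not necessarily counted as alive.** A reader might infer that missed deaths become survivors and that mortality is therefore understated. No section says so. SAP 6.1.5 specifies LOCF for clinical and microbiological outcome, leaves other variables unimputed, and does not say where vital status belongs. The supported finding is that the handling is unspecified.

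**Most subjects are already covered.** This also stands, as the table of contacts shows. It would be wrong to say that the plan follows its early leavers but not its completers in general.

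**Footnote 17 may concern early termination only.** In the extracted column heading its mark follows those words. That reading is possible, but a day of termination is hardly a specified date, whereas Day 28 is one. If the sponsor meant the narrower reading, the footnote still needs to say so.

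**Two-sided windows are convenient.** They are, for sampling and examination. That does not require vital and AE status to be closed early as well. Nor is there any argument that the gap would differ between blinded arms.

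**Conclusion.** The point holds in a limited form. On the more natural reading of footnote 17, a cured subject who attends on Day 26 or 27 has completed the study as planned, with no required check on or after Day 28. That does not fit a mortality endpoint tested at Day 28, a safety period running to 28 days after the dose, or the forward-only call for early leavers.

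The effect is small. The ceiling is 1.5-3.1 deaths among 154 subjects, resting on an assumed Day 28 mortality of 15-35%, a constant hazard, every subject closed on Day 26 and no later information. With only part of the subjects seen early and a lower hazard among the cured, about one death or fewer is realistic; that last step is judgement, since the documents give neither the timing of visits nor the mortality. The number of AEs at risk cannot be estimated from the documents. The Day 21 primary endpoint, the sample size and the type I error rate are unaffected. This is a low-cost correction of an internal inconsistency, not a threat to the trial's main conclusion.

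**What to change.** Either of two changes to footnote 17 in Protocol Table 6-1 and SAP Table 1 closes the gap:

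1. Make the final visit window forward only: Day 28, +2 days.
2. Keep ± 2 days for samples and examination, but for any subject seen on Day 26 or 27 require vital status, date of death and AE/SAE status to be confirmed on or after Day 28, by chart check or by the call mechanism already in Protocol 8.8.

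In either case, state that the footnote applies to the Day 28 visit, and add one sentence to the SAP saying how a subject whose vital status is last known on Day 26 or 27 enters the Day 28 mortality analysis.

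Cost: a line in the footnote and a sentence in the SAP. In practice, a few visits fall 1-2 days later under the first option, or a few subjects need a short call or chart check under the second.

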
6.1 Informed Consent

Informed consent will be obtained prior to any study-related procedure or data collection according to the regulations applicable at the study site where the patient is being enrolled. Depending upon such regulations, informed consent may be given by the study subject, a legally authorized representative, an independent physician or a council of independent physicians. The informed consent process will be duly documented in the subject's study file.

Prior to signing this document, the patient and/or his/her representative must have an opportunity to read it thoroughly, ask any questions, and do so under no pressure. The Informed Consent Form (ICF) should be provided to the patients as soon as possible before the first study procedures, so that time is allowed for each patient or his/her representative to review the documents and discuss them at his/her leisure.

If for any reason, the Informed Consent Form can only be read to the patient prior to his/her signing, a witness must sign, together with the patient, to guarantee that the document has been read to and understood by the patient prior to his/her signature.

The Investigator is responsible for obtaining the Informed Consent. If this task is delegated to other study personnel, the Investigator remains responsible for ensuring that the Informed Consent process has been followed and clearly documented.

